One method to attack these deficiencies in current program practice is to attack the time component of the hemostasis equation. In doing so, it is hypothesized that if radial artery compression time can be shortened to 40 minutes or less, the following could result: improved catheterization lab efficiency, greater patient satisfaction and lower complication rates, including RAO, may be improved. As concerns improved cath lab efficiency, a system that standardizes compression technique and shortens compression time to that which is fully under the supervision and care of cath lab holding room personnel, will also eliminate the variability of recovery staff needing to manage the hemostasis band / site, and complications typically associated with patient management being carried out in multiple settings within the hospital. To summarize, the potential advantages of a hemostasis system for PCI incorporating the benefits of the StatSeal technology used in combination with a hemostasis band as compared to a hemostasis band alone may include:

- Decreased radial artery compression times, aka Band In Place (BIP) time.
- Decreased incidence of RAO complications at discharge, or 24 hours, whichever occurs first
- Decreased incidence of other complications associated with TRA, such as hematoma, bleeding, and oozing.
- Elimination or reduction in the need for additional equipment, such as Doppler units, plethysmographs and pulse oximeters to assess hemostasis band efficacy
- Facilitate arterial site management to the more specialized catheterization lab staff/personnel that are better trained to recognize complications that occur during (BIP) band in place time.
- Decreasing the workload to the staff by virtue of shortened band in place times and improve procedural throughput.
- Facilitate greater patient comfort resulting from decrease band in place time and faster wound healing.

To do so, the effects of anticoagulation used during a PCI must be taken in to account.

II. DESCRIPTION OF THE STUDY DEVICE:

Recently, a new compound – potassium ferrate, in combination with a hydrophylic polymer which is formed in to a disc when compressed - has been used in conjunction with hemostasis bands to shorten compression times. This product (trade name StatSeal Advanced) is an FDA

approved product comprised of a topical hydrophilic polymer and potassium ferrate disc, [Photo 1] formed by compression of the compound.

Photo 1: StatSeal Advanced Disc

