- Cardiogenic shock or any clinical instability as assessed by the physician performing the procedure.

Transradial Catheterization Procedure

Transradial Cardiac Catheterization will be performed according to local practice standards with use of a sheath diameter of up to 6 Fr. (A 7Fr-in-6 Glidesheath Slender®, with an outer diameter of 6Fr is defined as a 6F sheath and is allowed.) In accordance with current recommendations for minimizing radial artery occlusion, a minimum of 5,000 units of unfractionated heparin, or therapeutic bolus of bivalirudin, will be administered to all patients enrolled in the study.

Patients will have their activated clotting time measured at least 5 minutes following the initial dose of anticoagulant, although every patient receiving 5,000 units of heparin will be eligible for the study. Vasodilators (nitroglycerin, verapamil) will be administered in accordance with local practice.

Timing of Subject Enrollment

A subject will be consented into the study prior to the administration of sedation prior to the procedure, and randomized at the conclusion of a successful procedure (after all anticoagulation and antiplatelet medication decisions have been made), at which time placement of the assigned HMS device will occur. Eligibility for the study will be assessed at this time and the subject will have to meet all of the inclusion criteria and none of the exclusion criteria.

Randomization will be performed by means of sealed envelopes in randomization blocks of 30. Each envelope will be labeled by patient number containing device designation. Device designation in the envelopes will be random in occurrence. When a patient is officially enrolled (after successful completion of a TRA procedure), the envelope corresponding to that patient number in the Study Patient log will be pulled, opened, and the assignment revealed.

Each of 4 sites will be allotted an initial block of 30 envelopes, and sets of backup blocks of 30 envelopes. On the discretion of the site principal investigator and the lead principal investigator, enrollment may continue until each site enrolls 30 patients. The maximum enrollment at any one site shall not exceed 50% of the total study enrollment, or 90 patients.

End of Study Status / Effect of Withdrawals:

A subject will have completed the study when one of the following events is documented:

1. The patient is successfully enrolled, treated with a HMS, and completes all required follow up tests.

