2. A subject withdraws consent to participate. Patients who withdraw from the study will be replaced and excluded from data analysis.

[figure not shown]
Protocol:

Control patients: Patients will have a TR band applied over the arteriotomy site and inflated with 15-18ml of air. After aspirating and clearing the contents of the sheath, the radial sheath will be removed. The TR band will be deflated until bleeding occurs, and 2 ml of air will be reintroduced to provide hemostasis. Patent hemostasis will be documented with plethysmography and oximetry as described below within 5 minutes after band application and removal, and within 30 min of discharge or after 24 hours. The TR band will be left inflated and in place for 2 hours following the procedure for all patients (regardless of diagnostic or PCI procedure), after which deflation attempts will commence.

Statseal Protocol: Patients will have a Statseal Advance (SSA) disc applied after withdrawing the radial sheath 2-4 cm. A Tegaderm dressing will be applied to secure the disc position. The TR band will be applied over the SSA disc with the center of the balloon (the green dot) over the center of the SSA disc. The TR band will be inflated with 8cc of air (which is typically occlusive pressure), and the sheath removed. No deflation will occur immediately. After 20 minutes of pressure, 3 cc of air will be removed from the TR band. After an additional 20 minutes (40 minutes after procedure), the TR band will be completely deflated, and the TR band left in place. After an additional 20 minutes (60 minutes after procedure) the TR band will be removed.

[rest of page intentionally blank]

STUDY OVERVIEW GRAPHIC

V. STUDY ACTIVITIES & GUIDELINES

Inspection Prior to Use

Prior to initiating any study activities, inspect the HMS devices for any damage. Do not use any device that appears compromised or damaged.

Required Accessories for each experiment

- Hemostasis Band (TR Band, Terumo, Inc.)
- StatSeal Advanced disc (if randomized to test group)
- Pulse oximeter

ACTIVITIES AND ASSESSMENTS

Informed Consent:

Subjects must have read the contents of the written informed consent document, had all questions regarding the study adequately answered by study staff, and signed and dated the document prior to any study related activities. See Appendix 1 for a sample of the Informed Consent document.

Definitions of Baseline and Procedural Variables:

Smoking: Active smoking or >20 pack year tobacco history.

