Diabetes: Hgb A1C >6.5% or active medical treatment for diabetes.

Hypercholesterolemia: LDL >130 or on treatment with antilipemic agents.

Hypertension: >140/80 or on medical treatment for hypertension.

Diagnostic procedure: Involving diagnostic catheters only.

Interventional procedure: Involving an interventional wire and therapeutic ACT typically >200, including for fractional flow reserve measurement where a stent is not placed.

Single wall puncture: Use of micropuncture wire and anterior wall puncture only.

Double wall puncture: Use of double wall puncture and sheath withdrawal technique.

Number of forward attempts: Number of forward advancements of the needle required to obtain access (not number of separate punctures of skin).

Procedure Start Time: Time when lidocaine is administered, prior to first puncture attempt.

Procedure End Time: Time when sheath is removed.

Test methodology:

All Pleth-ox testing will be done by qualified personnel with results classified according to Barbeau test pattern classifications. [Barbeau, et al. *Evaluation of ulnopalmar arterial arches with pulse oximetry and plethysmography; comparison with the Allen's test in 1010 patients. Am Heart Journal; 2004; 147:489-493*]

At the start of the TRA procedure, prior to radial artery cannulation, a baseline Pleth-ox exam will be performed for all patients and recorded on the CRF. Ulnar compression will be applied to confirm that the radial artery is patent. Patients with a type D pattern exam will be excluded from the study.

At the conclusion of a successful transradial procedure, the patient will be randomized to either SSA or TRB, each device applied per protocol & IFU.

Following placement of the HMS system, Pleth-Ox exams will be performed at the following time points with results recorded in the CRFs.

- Within 5 minutes of initial HMS placement
- In the SSA (StatSeal Advanced) group, within 5 minutes of the first partial deflation (20 minutes after initial placement).
- Within 5 minutes of full deflation of the HMS in both groups
- Within 30' of discharge or 24 hours post procedure (\pm 1 hour), whichever occurs first.

VI. STUDY STATISTICAL PLAN:

This is a physician initiated, prospective, randomized, two-arm study, to be conducted at up to four experienced 'Radial First' centers with the principal investigator having a (minimum) ten case experience using StatSeal Advanced.

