The sample size of 120 patients is estimated to have 90% power to detect an average difference in time to removal of the TR band of 60 minutes between the SSA and TRB groups, using a relatively large standard deviation of 100 minutes and a two-sided alpha of 0.05.

Descriptive summary statistics will be presented for all study variables. Continuous variables will be displayed as means with standard deviations and medians with 75th and 25th percentiles. Categorical variables will be summarized as frequencies with their respective percentages with two-sided 95% exact confidence intervals of the percentages. Statistical comparisons for continuous variables will be performed using the Student's t test or Mann-Whitney U test, as appropriate. Comparisons for categorical variables will be performed using the Chi square test or Fisher exact test, as appropriate. A two-sided P value of 0.05 will be considered statistically significant.

Categorical variables will include, but are not limited to:

- Percent of patients in each arm with total TTH of 60 minutes or less.
- Percent of patients in each arm with TTH of 40 minutes or less without complication.
- The percentage of patients in each arm with bleeding, oozing or hematoma during TTH, further delineated by the EASY bleeding and hematoma classification attached.
- Percent of patients in each arm with RAO at each /all follow-up points.
- Percent of patients in each arm with radial patency as tested with Pleth-ox at each designated test time point.

Primary Efficacy Outcomes:

In each arm the:

- Total Time to Hemostasis (TTH), defined as the total time the HMS applies compressive force until successful hemostasis is achieved without complication.

Secondary Efficacy Outcomes:

In each arm the:

- Percent of patients free from radial artery occlusion at discharge or at 24 hours, whichever occurs first.
- Percent of patients with Barbeau test patterns A,B,C,D at initial application of the HMS
- Percent of SSA patients with Barbeau test patterns A,B,C,D after 20' of HMS time.
- Percent of patients with Barbeau test patterns A,B,C,D at full deflation of the HMS. (40' for SSA group; per protocol in the TRB group)
- Percent of patients with Barbeau test patterns A,B,C,D at discharge or at 24 hours, whichever occurs first.
- Percent of patients in whom successful hemostasis is achieved in one hour or less.

Primary Safety Outcome:

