A PROSPECTIVE RANDOMIZED STUDY COMPARING THE INCIDENCE OF RADIAL ARTERY OCCLUSION (RAO) AND THE TIME TO HEMOSTASIS (TTH) WHEN USING A HEMOSTASIS BAND ALONE AND IN CONJUNCTION WITH A DISC COMPRISED OF POTASSIUM FERRATE (STATSEAL ADVANCED) FOLLOWING TRANSRADIAL CATHETERIZATION. Study Sponsor: A Physician Initiated Study

Principal Investigator: [name], MPA

Cardiology Division Veterans Medical Center Long Beach

Statistical Analysis

Continuous data are presented as mean \pm standard deviation and as median [interquartile range], and compared using unpaired t-test and Mann-Whitney U-test, respectively. Discrete data are presented as frequencies with their respective percentages and compared using Fisher's exact test. Outcome data were analyzed on an intention-to-treat basis. Two-tailed tests of significance are reported and p values < 0.05 were considered statistically significant. Univariate logistic regression was performed using all baseline patient and procedural variables available to predict the secondary outcome of hematoma formation. Variables that were significant in univariate analysis at $p<0.25$ were retained and entered into a multivariate model with a threshold of $p<0.05$ being considered as significant. Statistical analyses were performed using the SPSS statistical software program (SPSS version 16.0.2, Chicago, IL).

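### Adjusting the primary TTH comparison for procedure type, which is fixed before randomization, would be a small and nearly free gain in precision

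*Protocol*

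**What the plan says.** - **Population.** Protocol section IV enrolls diagnostic and PCI patients together, on unfractionated heparin or bivalirudin. The expected PCI share is not stated.
- **Procedure type is a defined variable.** Section V lists diagnostic and interventional procedures among the baseline and procedural variables: "Interventional procedure: Involving an interventional wire and therapeutic ACT typically >200".
- **It is known before allocation.** Under Timing of Subject Enrollment (section IV), patients are randomized once the procedure has succeeded and the anticoagulant and antiplatelet decisions are settled. Envelopes come in blocks of 30 allotted to each site, with no stratum for procedure type.
- **Background link to band time.** The Clinical Need says bands usually stay on at least 4 hours after PCI because of anticoagulation. The list of potential advantages of a hemostasis system for PCI closes with "To do so, the effects of anticoagulation used during a PCI must be taken in to account".
- **Schedules in the trial.** Control bands stay inflated for 2 hours before deflation attempts begin, "regardless of diagnostic or PCI procedure". In the StatSeal (SSA) arm full deflation is at 40 minutes for everyone.
- **Analysis.** Section VI names a t-test or Mann-Whitney test for continuous outcomes. In the SAP they are "compared using unpaired t-test and Mann-Whitney U-test, respectively". The SAP's only covariate model is a logistic regression for hematoma.

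**The concern.** If interventional patients need longer compression than diagnostic patients, procedure type explains part of the spread in TTH. An unadjusted test leaves that part in the error term. A chance difference in PCI share between arms then feeds into the estimated TTH difference, and the confidence interval is wider than it need be. Because procedure type is settled before allocation, adjusting for it cannot introduce post-randomization bias.

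Precision and credibility are at stake, not validity. If the arms turn out to differ in PCI share, an adjustment chosen after seeing this would look data-driven, whereas a pre-specified one would not.

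**Working it through.** **Inputs from the documents** (section VI, with 60 per arm from section IV): 120 patients in total, 90% power and a mean difference of 60 minutes. The spread and error rate are given as "using a relatively large standard deviation of 100 minutes and a two-sided alpha of 0.05". That calculation is for time to band removal. I carry its SD of 100 minutes over to TTH.

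**Assumptions not in the documents:** PCI share p of 0.3 to 0.5; PCI-minus-diagnostic gap in TTH, averaged over the two arms, D of 30 or 60 minutes.

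**1. The plan's own figure.** n per arm = 2 × (1.96 + 1.2816)² × (100/60)² = 58.4, so 59, or 118 in total. The exact noncentral-t calculation gives 60 per arm, 120 in total, with power 90.3%. The stated size reproduces.

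**2. Unadjusted precision.** SE = 100 × √(2/60) = 18.26 minutes. The 95% half-width is 1.96 × 18.26 = 35.8 minutes.

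**3. Chance imbalance.** At p = 0.5 the SD of the between-arm difference in PCI share is √(2 × 0.25/60) = 0.0913, so the 95% range is ±1.96 × 0.0913 = ±0.179. The shift in the TTH difference is D times this: 30 × 0.179 = 5.4 minutes and 60 × 0.179 = 10.7 minutes. From exact binomials, the arms differ by at least 10 percentage points in 27% (p = 0.3) to 32% (p = 0.5) of trials.

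**4. Gain from adjustment.** Share of variance explained: R² = p(1 − p)D²/100². Residual SD = 100 × √(1 − R²). Power uses the noncentral t at 60 per arm for 60 minutes.

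| p | D (min) | R² | Residual SD | SE | 95% half-width | Power | 95% shift removed |
|---|---|---|---|---|---|---|---|
| none | 0 | 0 | 100 | 18.26 | 35.8 | 90.3% | none |
| 0.3 | 30 | 0.019 | 99.0 | 18.1 | 35.4 | 90.8% | ±4.9 |
| 0.3 | 60 | 0.076 | 96.1 | 17.6 | 34.4 | 92.4% | ±9.8 |
| 0.5 | 30 | 0.023 | 98.9 | 18.1 | 35.4 | 90.9% | ±5.4 |
| 0.5 | 60 | 0.090 | 95.4 | 17.4 | 34.1 | 92.7% | ±10.7 |

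**5. The shift and the wider interval are one cost, not two.** At p = 0.5 and D = 60, the SD of the shift is 60 × 0.0913 = 5.48 minutes, and 17.42² + 5.48² = 333.5, which matches 18.26² = 333.4. The unadjusted standard error already contains the chance imbalance.

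**6. Simulation** (20,000 trials per setting, p = 0.5, D = 60). The unadjusted test has type I error 5.2% and a mean estimate of −60.0 minutes when the true difference is −60. Power is 90.5% unadjusted and 92.8% adjusted.

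**The case against.** The case for leaving the plan alone is strong on most counts.

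- **A reader might infer that the plan breaks its own rule.** It does not. The anticoagulation sentence ends a background list and says what a hemostasis system for PCI has to cope with. The next section introduces the disc. Neither document promises an adjusted analysis.
- **A reader might infer that the primary comparison is biased or underpowered.** Randomization makes the unadjusted comparison unbiased, its error rate is 5%, and 120 patients give about 90% power without adjustment. At the permitted maximum of 180 patients (90 per arm) power is already 97.9%.
- **A reader might take the background's 4-hour figure as a large gap in this trial.** Section IV sets one schedule per arm regardless of procedure type, and section II describes a seal that does not depend on clotting. Any gap should therefore sit mainly in controls after the 2-hour mark. An arm-averaged gap of 60 minutes already corresponds to a 120-minute gap in controls and none in the SSA arm. An average of 120 would need PCI controls to run 240 minutes longer than diagnostic controls. I do not rely on that scenario. The 1-3 hours of typical local use in section IX does not establish a gap either, because it is not specific to diagnostic cases.
- **A reader might infer that anticoagulation is inadequately recorded**, since the stated requirement is "Patients will have their activated clotting time measured at least 5 minutes following the initial dose of anticoagulant". The case report forms are not available, so what else is captured is unknown, and no new data field is justified on this ground.

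What remains is that section IV fixes only when control deflation attempts begin, not when they succeed, and the plan itself expects an SD of 100 minutes. Room is left for procedure type to matter, and the planned analysis does not use it.

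**Conclusion.** The point holds as a minor efficiency matter. The TTH comparison is valid, but it ignores a baseline factor that is known before allocation, not balanced by design, and linked to band time in the protocol's own background. On the assumptions above, adjustment adds about 0.6 to 2.4 percentage points of power at a 50% PCI share (90.3% to 90.9-92.7%). It takes at most about 2 minutes off the half-width and removes chance shifts of up to about 5 to 11 minutes, against a target difference of 60. The size rests on an assumed gap and PCI share and on applying the plan's SD to TTH. If the gap is near zero, the gain is near zero and almost nothing is lost.

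**What to change.** In the SAP, pre-specify that the TTH difference is estimated with a linear model containing arm, procedure type (as defined in protocol section V) and site, the factor on which the envelopes are blocked. Use robust standard errors, because the fixed schedules are likely to make TTH skewed and its spread unequal between arms. Keep the Mann-Whitney test as a sensitivity analysis.

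Report the TTH and access-site bleeding differences with confidence intervals separately for diagnostic and PCI patients, together with an arm-by-procedure interaction estimate. The interaction term is needed because a model with arm and procedure type alone cannot show whether the benefit differs by procedure. Label these results supportive and imprecise. At 30 per arm in each stratum (assumed 50% PCI) and SD 100, the half-width within a stratum is 1.96 × 100 × √(2/30) = 51 minutes, and for the interaction √2 times that, about 72 minutes.

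The cost is a few sentences of SAP text, with no added patients or procedures, since procedure type is already a defined study variable. The SAP is worded in the past tense; if outcome data had already been seen, the adjusted estimate should be shown beside the planned test and labelled post hoc.

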When in the direct contact with even a small amount of blood, the compound forms an occlusive seal through simultaneous iron-mediated agglomeration of blood solids/proteins and rapid dehydration of the blood. Seal formation is independent of the clotting cascade, facilitating sealing regardless of anticoagulation / antiplatelet status of the patient. Following cessation of pressure being applied to the site, the remnants of StatSeal form what resemble a 'scab', and remains in place for 24 hours, covered with a band-aid or Tegaderm patch.

In clinical testing using a protocol refined at the University of Miami Miller School of Medicine, the use of this compound in conjunction with commercially available hemostasis bands has demonstrated the potential to significantly shorten the time required to achieve hemostasis^{11,12}. Further, these results demonstrated the ability to achieve hemostasis using StatSeal with similar, or fewer complications when compared to standard methods, and did so regardless of the patient's anticoagulation status.

INDICATION FOR USE

StatSeal Advanced is a commercially available product in the United States, and is indicated for use on patients in whom the radial artery has been used to gain vascular access for a cardiovascular procedure.

DEVICE STORAGE AND ACCOUNTABILITY

StatSeal Advanced is provided in a sterile, foil pouch to protect it from humidity / moisture. As with most medical products, it should be stored in a cool, dry, secure environment. StatSeal Advance will be provided at no charge by the manufacturer for use in the study.

Damaged devices will be returned to the manufacturer (Biolife, LLC, Sarasota,FL). All unused devices may be retained by the site for continued use, if they so choose.

III. STUDY OBJECTIVE(S)

The primary objectives of this study are to evaluate the performance of StatSeal Advanced used in conjunction with the TR Band (SSA) as compared to the TR Band without SSA (TRB) relative to:

1. the incidence of peri-procedural radial artery occlusion (RAO) at discharge or 24 hours, whichever occurs first, and;
2. the Time to Hemostasis (TTH)

HMS is defined as the Hemostasis Management System employed based on which group the patient is randomized to (either SSA or TRB).

Radial Artery Occlusion is defined as the absence of flow to the hand based upon plethysmography – pulse oximetry (Pleth-Ox) performed using the Barbeau scale.

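### RAO is a primary objective in Section III but a secondary outcome in Section VI, and the SAP names no primary outcome

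*Protocol*

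**What the plan says.** - **Protocol, Section III (Study Objectives).** Two primary objectives are listed. The first is "the incidence of peri-procedural radial artery occlusion (RAO) at discharge or 24 hours, whichever occurs first"; the second is TTH.
- **Protocol, Section VI, Primary Efficacy Outcomes.** There is one entry: "Total Time to Hemostasis (TTH), defined as the total time the HMS applies compressive force until successful hemostasis is achieved without complication".
- **Protocol, Section VI, Secondary Efficacy Outcomes.** The first entry is "Percent of patients free from radial artery occlusion at discharge or at 24 hours, whichever occurs first".
- **Protocol, Section VI, Primary Safety Outcome.** This covers access-site complications and expressly leaves RAO out, so RAO is not primary anywhere in Section VI.
- **Protocol, Section VI, sample size.** "The sample size of 120 patients is estimated to have 90% power to detect an average difference in time to removal of the TR band". The assumed difference is 60 minutes, with SD 100 minutes and two-sided alpha 0.05. No RAO rate, effect or power is given.
- **Protocol, Section VI, tests and intervals.** "Comparisons for categorical variables will be performed using the Chi square test or Fisher exact test, as appropriate". Percentages are to be shown "with two-sided 95% exact confidence intervals of the percentages"; these are per-arm intervals, and none is planned for the difference between arms.
- **SAP.** The title names RAO and then TTH without ranking them, and the text designates no primary outcome. The only outcome it ranks is hematoma, called secondary. Discrete data are "compared using Fisher's exact test", and "p values < 0.05 were considered statistically significant".

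**The concern.** The same measure at the same time point is primary in one section and secondary in another, and nothing reconciles the two. There is no co-primary rule and no multiplicity adjustment. A low RAO p-value could be presented as a primary finding under Section III, and a high one set aside as secondary under Section VI. RAO is one of the two questions in the study title, so this affects the main claim of the trial.

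A second risk follows. Neither document plans an equivalence claim for RAO. But with no stated limit and no interval for the difference, a non-significant test invites the reading that the two methods have similar RAO rates. A trial of this size could not support that reading.

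**Working it through.** **1. Which reading does the sample size fit?** Inputs from Section VI: difference 60 min, SD 100 min, two-sided alpha 0.05, power 90%.

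n per arm = 2(1.960 + 1.282)² × 100² / 60² = 58.4, rounded up to 59, or 118 in total. The t-test version gives 59.4, so 60 per arm and 120 in total. Power at 60 per arm is 90.8% (normal) or 90.3% (t). The plan's figure of 120 reproduces, and it is a calculation for a time outcome only.

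**2. What power would RAO have as a primary?** The plan gives no target effect, so one must be assumed. The Background gives RAO in about 5-10% of cases; I take a halving as the base case and larger effects as a range. Arm sizes are 60 (the stated minimum) and 90 (half of the maximum of 180, assuming 1:1 allocation holds). Power is the sum of the two binomial probabilities over every table with two-sided p<0.05.

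| TRB vs SSA | Fisher, 60 / 90 per arm | Chi-square (uncorrected), 60 / 90 per arm |
|---|---|---|
| 10% vs 5% | 8.8% / 17.1% | 17.4% / 24.0% |
| 5% vs 2.5% | 2.1% / 5.5% | 9.3% / 12.2% |
| 10% vs 1% | 39.8% / 70.0% | 62.8% / 80.9% |
| 10% vs 0% | 56.3% / 89.7% | 86.3% / 98.3% |
| 5% vs 0% | 7.9% / 29.5% | 35.3% / 66.4% |

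For a halving, power is below 25% in every cell. With no occlusions in the SSA arm, Fisher's test needs at least six in the TRB arm: 0/60 vs 5/60 gives p = 0.057 and 0/60 vs 6/60 gives p = 0.027; 0/90 vs 5/90 gives p = 0.059 and 0/90 vs 6/90 gives p = 0.029.

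**3. What size would RAO need?** Pooled two-proportion formula, 80% power, alpha 0.05:

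n = [1.960√(2p̄(1−p̄)) + 0.842√(p₁(1−p₁) + p₂(1−p₂))]² / (p₁−p₂)²

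- 10% vs 5%, p̄ = 0.075: (0.7301 + 0.3121)² / 0.05² = 434.4, so 435 per arm.
- 5% vs 2.5%, p̄ = 0.0375: (0.5266 + 0.2256)² / 0.025² = 905.4, so 906 per arm.

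With continuity correction, which approximates Fisher's test, these become 474 and 984. Against 90 per arm, 435/90 = 4.8 and 906/90 = 10.1.

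**4. What would a non-significant result mean?** Illustration: 3/60 (SSA) vs 6/60 (TRB), Fisher p = 0.49, difference −5 points. The Wilson limits are 1.7-13.7% and 4.7-20.1%. The Newcombe interval is −5 − √(3.29² + 10.15²) = −15.7 to −5 + √(8.70² + 5.34²) = +5.2 points. Miettinen-Nurminen gives −15.9 to +5.2. The per-arm exact intervals that the plan already provides are 1.0-13.9% and 3.8-20.5%; they do not show the uncertainty of the difference.

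**5. What if both are primary and either suffices?** The family-wise error is 1 − 0.95² = 0.0975 if the tests are independent. Splitting alpha to 0.025 each lowers TTH power at 60 per arm to 84.4% (t-test); 90% power would then need 71 per arm. RAO would remain underpowered for a halving.

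**The case against.** An objective is not an outcome. Section VI is the operative list, it agrees in kind with the sample size, and the SAP is silent rather than opposed. On that view one section is simply out of line. This is fair as an account of what was probably intended, and it is why the fix follows Section VI. It does not remove the conflict: Section III uses the word primary for the same measure at the same time point, and the SAP, which should settle the matter, does not.

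The power figures depend on an assumed effect. That stands. If SSA nearly eliminated RAO from a 10% rate, 90 per arm would be adequate. The protocol also puts late occlusion below about 5% with the patent-hemostasis technique. Applying that to the control arm is a further assumption, because the figure is for late occlusion and the control arm's inflation steps differ from those described in the Background. The protocol offers lower RAO only as a possible benefit, so no effect can be taken as expected. The contradiction itself needs none of these figures.

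Demoting RAO is not the only inexpensive remedy. Testing TTH first and RAO only if TTH is significant, each at 0.05, also needs no extra patients. This is correct and compatible with the fix below.

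TTH has problems of its own. The trial is sized on time to band removal, whereas Section III excludes time with a fully deflated band. In the SSA arm these are nominally 60 and 40 minutes. Much of the difference between arms is also set by the scheduled deflation times. These are separate points; they do not make RAO a supportable primary at this size.

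**Conclusion.** The concern holds and must be fixed: the hierarchy is contradictory as written. The finding rests on the text of Sections III and VI and on the SAP's silence, not on the power calculations. Those show only that RAO cannot stay primary at 60 to 90 per arm unless near-elimination from a rate of about 10% is assumed. For a halving from 5-10%, power is 2.1-17.1% by Fisher and 9.3-24.0% by chi-square. The assumptions are the halving, the background range carried to discharge or 24 hours, and equal arms at the maximum enrollment.

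**What to change.** 1. Name TTH as the single primary efficacy outcome in Section III, Section VI and the SAP. It is the outcome closest to the one the trial is sized on; use one definition of it throughout.
2. Label RAO at discharge or 24 hours as the first key secondary outcome in all three places. Add a line under the SAP title giving this hierarchy, including the primary safety outcome. The SAP calls hematoma secondary, while the protocol counts Class III-V hematoma under primary safety; reconcile the two.
3. Report RAO as a risk difference (SSA minus TRB) with a 95% Newcombe or Miettinen-Nurminen interval, alongside the planned per-arm exact intervals. Show the Fisher p-value as supportive only. If a formal RAO test is wanted, place it after TTH in a fixed sequence.
4. State that the trial is not sized for RAO and that p>0.05 will not be reported as similar RAO.
5. Date the change. The SAP is written in the past tense, so also state whether comparative results had been seen when it was made.

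The cost is wording in three places and one interval, with no extra patients. The downside is that RAO can no longer be presented as a primary finding. Keeping RAO primary with its own sample size would take about 5 to 10 times the maximum of 90 per arm for a halving.
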